7.0 Study Withdrawal/Discontinuation

This study is voluntary and participants have the right to withdraw at anytime. Participants must notify the Principal Investigator that they choose to withdraw from the study:

[name], MPH
Indiana University Department of Surgery
Trauma and Emergency General Surgery
[name]
[name]
[contact]

Participants who choose to withdraw will be informed that no new procedures will be performed after receiving their notice that they choose to withdraw from the study. Information that has been obtained up to that point will remain as part of the study.

8.0 Statistical Considerations

We will compare randomization results to a pre-planned randomization schedule to ensure randomization integrity. To verify the comparability of the randomized groups, patients' baseline characteristics between the intervention and the usual care group will be compared using analysis of covariance (ANCOVA) for continuous variables and the Cochran-Mantel-Hansel statistic for categorical variables while adjusting for recruitment

sites. We will examine the distributions of continuous variables and use alternative approaches such as transformation or nonparametric methods in cases of violation to the normal distribution assumption. We will also examine the frequency distribution of all categorical variables and adopt exact inference procedures in cases of zero or small cell size. All analyses will be conducted using SAS 9.4 (SAS Institute, Cary, North Carolina).

Obective 1: Evaluate the ability of the TMH intervention to improve the physical recovery of the non-neurologically injured patient. Mixed effects models will be used with repeated physical function scores (SPPB and PCS on the SF-36) collected at baseline, 6 months and 12 months as the outcome measures, group, time, and a group and time interaction as independent variables while adjusting for stratification variables (recruitment site, injury severity and injury type) and other potential baseline covariates that are found to be different between the two groups. An unstructured variance-covariance matrix will be used in the mixed effects models to adjust for the potential correlations among SPPB and PCS obtained from the same individual over time. A significant interaction between group and time would indicate differences in changes of physical functions over time between the two groups. Post-hoc comparisons at each follow-up time will be conducted following a significant interaction between group and time to determine the time when a group difference can be detected. Parameter estimation and inference for the mixed-effects models are conducted using the maximum likelihood approach which are robust under many missing data mechanisms.⁷² We will also include additional covariates to examine whether patients' characteristics or prior medical comorbidities are associated with the changes in physical function scores.

Objective 2: Evaluate the ability of the TMH intervention to improve the psychological recovery of the non-neurologically injured patient. Mixed effects models will be used with repeated PHQ-9, GAD-7 or MCS on SF-36 scores as the outcome variables, group, time and interactions between group and time as independent variables while adjusting for stratification variables and other baseline covariates that may be different between the two groups, similar to the approach described for Aim 1. Post-hoc analyses will also be conducted following significant interactions in the mixed effects models to examine differences in psychological outcome measures between intervention and usual care groups at 6 and 12 months.

Objective 3: Evaluate the ability of the TMH intervention to reduce health cost and the TMH cost effectiveness relative to usual care of the non-neurologically injured patient. Economic Value and Costs. Time from enrollment to *emergency department visits and hospital readmissions* will be used as the outcome variables in Cox's proportional hazard models and group as the independent variable while adjusting for sites and other baseline covariates. Patients who are followed to 12 months without experiencing any event will have their event time censored at 12 months and patients who died or were lost to follow-up will have their observation time censored at time of death or date of last contact. The proportional hazard assumption will be examined by including the interaction between the group indicator variable and time.

We will conduct a cost effectiveness analysis to determine if changes in health care utilization offset the intervention costs between treatment arm and usual care. To conduct this analysis, we will use established methods to estimate direct costs of the interventions and health care spending from a Medicare payment perspective. The conceptual proposition begins with our proposed TMH intervention, which requires healthcare and non-healthcare resources for delivery (e.g., therapists or transportation) and caregiver assistance. The foregone economic opportunities and ability for

successful return to activities of daily living and participation can be assessed in combination with recovery time in dollar value. Changes in patients' health status, long-term mobility, and community participation will be assessed using the SF-36 tools for measuring physical functioning and utility.⁷³⁻⁷⁶ Changes in health status and community participation are captured. The cost effectiveness ratio is practically measured as the increment in cost summary to the increment in the effect measure.

Multivariate regression models will be constructed to examine total healthcare costs in the 12-month post index period. To address issues of skewness and violations of normality assumptions, and medical comorbidities, a generalized linear model with a gamma distribution and a log-link function will be used. Estimated parameters will be obtained using the maximum likelihood technique,⁷⁷⁻⁸¹ and adjusted results will be presented with 95% confidence interval (CI) estimates. Finally, the incremental cost to achieve a clinically meaningful change in SF-36 scores due to the interventions, i.e., the cost-effectiveness (CE) ratio, is the difference in intervention costs of the treatment arms, divided by the difference in effectiveness between groups; or

$$CE\ ratio = \frac{TMH\ Intervention\ costs + \delta(\ Health\ care\ and\ opportunity\ costs)}{\delta\ SF - 36\ (TMH) - \delta\ SF - 36\ (Usual\ Care)}$$

Sensitivity analysis of all key assumptions and bootstrapping will be conducted. All analyses were conducted with Statistical Analysis Software (SAS, Version 9.3, Cary, NC).⁴⁶

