study is not powered to detect significant treatment effect within each randomization stratum unless there are large effect sizes in each stratum. Instead, stratified randomization was used to control for potential heterogeneity in patient outcomes in order to detect a significant treatment effect in the overall sample. Since we will have access to the electronic medical records on all enrolled patients, for the analysis on acute care utilization, data on all 430 randomized patients will be retrieved to determine status and time to ER visits and re-hospitalization. We will have 80% power to detect odds ratio of 1.8 or greater for ER visits assuming cumulative event rate of 25% in the usual care group and 82% power to detect odds ratio of 1.9 or greater for re-hospitalization assuming cumulative event rate of 20% in the usual care group using Chi-squared test at the 0.05 significance level.

Potential Problems and Alternative Strategies.

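### Unless the stratification variables are crossed with time, adjusting for them does almost nothing for the group-by-time test, which is then conservative to the extent that the strata predict recovery

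*Combined protocol and SAP*

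**What the plan says.** All of this is in Section 8.0 of the combined protocol and SAP.

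- Objective 1 models SPPB and PCS "collected at baseline, 6 months and 12 months as the outcome measures", with "group, time, and a group and time interaction as independent variables while adjusting for stratification variables (recruitment site, injury severity and injury type"). Baseline covariates found to differ between the arms are also adjusted for. "An unstructured variance-covariance matrix will be used in the mixed effects models".
- The test is on change: "A significant interaction between group and time would indicate differences in changes of physical functions over time between the two groups". Comparisons at 6 and 12 months come only after a significant interaction.
- A further step is planned: "We will also include additional covariates to examine whether patients' characteristics or prior medical comorbidities are associated with the changes in physical function scores".
- The text for Objective 2 handles PHQ-9, GAD-7 and MCS "while adjusting for stratification variables and other baseline covariates that may be different between the two groups", and refers back to the approach for the first aim.
- Sample Size and Power gives the reason for stratifying: "stratified randomization was used to control for potential heterogeneity in patient outcomes in order to detect a significant treatment effect in the overall sample".

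The plan does not say whether any covariate enters as a main effect or crossed with time. It gives no figure for how strongly the strata predict either the level of a score or its change.

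**The concern.** Because baseline is one of the outcomes, the group-by-time term is a difference between arms in within-patient change. A covariate that does not vary over time and enters additively moves baseline, 6 and 12 months by the same amount. It therefore subtracts out of every change and cannot adjust the tested contrast.

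Two things are at stake. First, stratified allocation reduces the true variance of the estimate wherever the strata predict change. A model that ignores this reports a standard error that is too large, so intervals are too wide and the real type I error falls below 5%. Second, the plan relies on covariate adjustment to deal with baseline differences between the arms. Entered additively, that adjustment cannot correct the change contrast either. Both affect all five scores in Objectives 1 and 2.

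**Working it through.** **Step 1: the plan's own figure.** Inputs from Sample Size and Power: 150 completers per arm, a difference of 0.81 in SPPB change, SD 2.5 (stated for baseline and used as the SD of change), alpha 0.05 and 30% missing at 12 months. The test is taken as two-sided.

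- SE = 2.5 × √(2/150) = 0.2887
- Power = Φ(0.81/0.2887 − 1.96) = Φ(0.846) = 80.1%
- 150/0.70 = 214.3, so 215 per arm and 430 in all

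The figures reproduce. They come from an unadjusted two-sample comparison and credit nothing to the strata.

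**Step 2: why a main effect cancels.** Write the model as Y(i,t) = μ(t) + δ(t)·g(i) + γ·s(i) + e(i,t), with g the arm and s the strata. Then

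Y(i,12) − Y(i,0) = [μ(12) − μ(0)] + [δ(12) − δ(0)]·g(i) + [e(i,12) − e(i,0)].

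The term γ·s(i) is gone. With complete data and an unstructured covariance, the equations for change contain only an intercept and group. These are nested in the baseline equation, which adds the strata. The maximum-likelihood estimate of the interaction is then simply the raw difference in mean change.

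A simulated complete data set (300 patients, strata explaining 20% of the variance of change) confirms it. The 12-month interaction was 0.7910 with strata as main effects, 0.7910 with no strata, and 0.7910 as the raw difference. The SE was 0.2794 in both models. Crossing the strata with time reduced it to 0.2469.

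**Step 3: size for the 12-month contrast.** Let R² be the share of the variance of change that the strata explain. The documents give no value, so 0% to 20% is assumed, with allocation balanced within strata.

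- Model SE with main effects: 0.2887 throughout
- True SE, and SE with strata by time: 0.2887 × √(1 − R²)
- Excess interval width: 1/√(1 − R²) − 1
- True alpha with main effects: 2[1 − Φ(1.96/√(1 − R²))]
- Power with main effects: Φ((0.81 − 1.96 × 0.2887)/true SE)
- Power with strata by time: Φ(0.81/true SE − 1.96)

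| Assumed R² | True SE | Excess width | True alpha, main effects | Power, main effects | Power, strata by time |
|---|---|---|---|---|---|
| 0% | 0.289 | 0% | 5.0% | 80.1% | 80.1% |
| 5% | 0.281 | 2.6% | 4.4% | 80.7% | 82.1% |
| 10% | 0.274 | 5.4% | 3.9% | 81.4% | 84.1% |
| 20% | 0.258 | 11.8% | 2.8% | 82.8% | 88.0% |

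**Step 4: missing data.** Two simulations used 430 patients, about 30% missing at 12 months, R² of 20%, and permuted blocks in 8 strata, with 600 runs per setting.

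- In one, the model SE was 0.275 with no strata, 0.272 with main effects and 0.245 with strata by time. Type I error was 3.0%, 2.8% and 5.2%; power was 86.3%, 86.7% and 89.8%.
- In the other, main effects against strata by time gave SE 0.272 against 0.246, type I error 3.5% against 5.7%, and power 85.0% against 88.7%. At R² of 0 the SEs were 0.273 and 0.272.

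Simulation error is about 1 point on alpha and 1.5 points on power. One complete-data setting (R² 20%) gave 7.0% type I error for strata by time. Its mean model SE was 0.256 against the analytic 0.258, so the maximum-likelihood SE is slightly small. With a simulation SE of √(0.05 × 0.95/600) = 0.9 points, much of that excess may be chance.

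**Step 5: an imbalanced baseline covariate.** In one illustrative data set (150 per arm, no true effect, a covariate that predicts change and differs by 0.29 SD between arms), the raw difference in 12-month change was 0.8515. The main-effects model returned 0.8515. With covariate by time it was 0.509.

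**The case against.** Several stronger readings are tempting, and the documents do not support them.

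- *The plan specifies main effects only.* It does not; the form of adjustment is left open. Main effects is an inference, though the ordinary one when a single interaction is listed.
- *The benefit of stratifying is lost, or the trial is underpowered.* Balanced allocation still lowers the true variance. Power with main effects is at or slightly above the planned 80.1%, and the sample size counted no gain. Power is lower only than under the better model. The gap is also smaller with missing data: 3.1 points (89.8 − 86.7) or 3.7 (88.7 − 85.0), against 5.2 (88.0 − 82.8) in the table.
- *The intervals are too wide whatever the strata do.* If the strata shift all visits equally, the change contrast already removes them and the SE is right. The 20% case is also demanding. The between-strata SD would be √(0.20 × 6.25) = 1.12 points, which as an even two-way split is a 2.24-point gap in recovery. Section 5.0 expects a total SPPB improvement of only 8 − 6.0 = 2.0 by 12 months.
- *The exploratory step would test level instead of change.* Its stated purpose is association with changes, which implies covariate-by-time terms. The model is merely not written down.

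Two further objections stand. Additive strata are not useless elsewhere. With an assumed visit correlation of 0.5, the SE of the 12-month group difference fell from 0.284 to 0.252 when strata explained 20% of level variance, and from 0.286 to 0.269 at 10%. Those comparisons, however, are reached only after a significant interaction. Also, the figures are for the single 12-month contrast. With three categorical visits the interaction test has 2 degrees of freedom, and its error rate was not computed. The blocks and the 8 strata are assumptions too: Sections 3.0 and 4.0 name two hospitals, and Section 5.0 says three.

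**Conclusion.** The point holds in conditional form. Read in the ordinary way, the adjustment in Objectives 1 and 2 drops out of the group-by-time test, exactly with complete data and nearly so with 30% missing. Additive adjustment for imbalanced baseline covariates likewise leaves the change contrast uncorrected.

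For the strata the consequence is a conservative test, not bias or an inflated error rate. Its size rests on two assumptions: the share of the variance of change that the strata explain, and balanced allocation within strata. Over an assumed 0% to 20%, intervals for the 12-month contrast are 0% to about 12% wider than needed. The planned power and sample size stand. This is a cheap improvement, not a flaw that threatens the trial.

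**What to change.** In Section 8.0, Objectives 1 and 2, state that each stratification variable, and each baseline covariate that is kept, enters the mixed model together with its interaction with categorical time. State also that association with changes in scores is read from the covariate-by-time term.

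The cost is a line of SAP wording and a few model degrees of freedom. For three two-level stratification variables and two follow-up visits that is 3 × 2 = 6 extra parameters, or (2 + 1 + 1) × 2 = 8 if there are three hospitals. No new data are needed. If the strata do not predict change, the SE is practically unchanged.

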Primary hypothesis: In comparison to the older injury survivors randomized to usual care, those randomized to the TMH intervention will have the following at 6 and 12-month follow-ups:

- *Higher physical performance as measured by the short physical performance battery (SPPB);*
- *Higher scores on the Physical Component Summary (PCS) of the Medical Outcomes Study 36-time short form (SF-36).*

Secondary Objectives:

1: Evaluate the ability of the TMH intervention to improve the psychological recovery of older injury survivors.

Secondary hypothesis 1: In comparison to older injury survivors randomized to usual care, those who are randomized to the TMH intervention will have the following at 6 and 12-month follow-ups:

- *Lower mood and anxiety symptoms as measured by the Patient Health Questionnaire-9 (PHQ-9) and the Generalized Anxiety Disorder (GAD-7) scale;*
- *Higher scores on the Mental Component Summary (MCS) of the SF-36.*

2: Evaluate the ability of the TMH intervention to reduce health care cost of older injury survivors and evaluate the cost effectiveness of TMH.

Secondary hypothesis 2: In comparison to older injury survivors randomized to usual care, those who are randomized to the TMH intervention will have the following at 6 and 12-month follow-ups:

- *Lower emergency department and hospital related cost.*
- *Savings in healthcare utilization in the intervention arm that will offset the intervention costs.]*

Due to demographic shifts, changes in life expectancy and increased activity of older Americans – putting them at risk for injury – there is an urgent need to enhance the recovery care for older injury survivors. Trauma centers across the nation are in an extraordinary position to use the information generated from the proposed trial to intervene; so older injury survivors may enjoy the maximum level of functional ability and quality of life after injury.

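### Under the displayed formula, the hypothesised economic success gives a zero or negative cost-effectiveness ratio; the plan should add net benefit, a dominance rule and a joint cost-effect presentation

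*Combined protocol and SAP*

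**What the plan says.** Section 2.0, secondary hypothesis 2, expects "Lower emergency department and hospital related cost" and "Savings in healthcare utilization in the intervention arm that will offset the intervention costs". The primary hypothesis and secondary hypothesis 1 expect higher SF-36 summary scores under TMH, for example "Higher scores on the Mental Component Summary (MCS) of the SF-36".

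Section 8.0, Objective 3, describes the ratio in three ways:

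- In general terms: "The cost effectiveness ratio is practically measured as the increment in cost summary to the increment in the effect measure".
- In the sentence that begins "Finally, the incremental cost to achieve a clinically meaningful change in SF-36 scores due to the interventions, i.e., the cost-effectiveness (CE) ratio", which goes on to put only the arms' difference in intervention costs over the difference in effectiveness.
- In the displayed formula, whose numerator is TMH intervention cost plus the change in health care and opportunity costs, and whose denominator is the SF-36 change under TMH minus that under usual care.

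Costs are modelled as "total healthcare costs in the 12-month post index period". The formula states neither the SF-36 component nor the time point of the change. On uncertainty, the section says only: "Sensitivity analysis of all key assumptions and bootstrapping will be conducted". There is no dominance rule, cost-effectiveness plane, net-benefit analysis, acceptability curve or value per unit of effect.

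**The concern.** A cost-effectiveness ratio is useful when the new intervention costs more and does more, because it then gives the price of an extra unit of effect. This trial hopes for the opposite cost result: TMH pays for itself and patients do better. In that region a smaller or larger ratio is not a better or worse result, and the same negative number can describe a clear success or a clear failure. Resampling a ratio adds a further difficulty when the denominator can be close to zero.

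At stake is the summary statistic of a secondary objective. As planned, it would be least informative in the case the trial is designed to show.

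**Working it through.** **1. The plan's own sample size (Section 8.0, Sample Size and Power).** For SPPB, SD 2.5, difference 0.81, two-sided alpha 0.05, 80% power: n = 2 × (1.960 + 0.842)² × (2.5/0.81)² = 149.5, so 150 per arm. Allowing 30% missing, 150/0.70 = 214.3, so 215 per arm and 430 in all. At 0.325 SD with 150 per arm, t-test power is 80.1%. The plan's figures reproduce, and 150 per arm is used below. The plan gives no cost figure to reproduce.

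**2. Sign of the ratio.** Write the displayed formula as R = ΔC/ΔE, where ΔC = TMH cost + change in other costs.

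- Higher SF-36 under TMH: ΔE > 0.
- Savings offset TMH cost: ΔC ≤ 0, strictly negative only if savings exceed TMH cost. The hypotheses do not sign opportunity costs, so these are left aside.
- Hence R ≤ 0.

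Under the sentence's narrower numerator (intervention costs only), R would be positive if TMH costs more to deliver. The two definitions can therefore differ in sign.

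**3. Order.** Illustrative dollars; net benefit is value × ΔE − ΔC, at an illustrative $500 per point:

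| ΔC | ΔE (points) | R per point | Net benefit |
|---|---|---|---|
| −1,000 | 0.5 | −2,000 | 1,250 |
| −1,000 | 1 | −1,000 | 1,500 |
| −1,000 | 4 | −250 | 3,000 |
| −4,000 | 4 | −1,000 | 6,000 |
| +1,000 | −1 | −1,000 | −1,500 |

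At a fixed saving, a larger gain moves R towards zero. Three quite different results share R = −1,000, and one of them is dearer and worse. Net benefit orders all five.

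**4. Precision of the denominator.** PCS SD is 5 (Section 5.0, Outcome Measures). With correlation r between baseline and follow-up, the SD of change is 5 × √(2(1 − r)). At the assumed r = 0.5 this is 5, so SE(ΔE) = 5 × √(2/150) = 0.577. The design effect is 0.325 × 5 = 1.625 points.

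The probability that the 95% CI of ΔE includes zero is Φ(1.96 − ΔE/SE) − Φ(−1.96 − ΔE/SE):

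| True ΔE | r = 0.3 (SE 0.683) | r = 0.5 (SE 0.577) | r = 0.7 (SE 0.447) |
|---|---|---|---|
| 1.625 | 34% | 20% | 5% |
| 0.81 | 78% | 71% | 56% |
| 0 | 95% | 95% | 95% |

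When that CI includes zero, a Fieller-type interval for R is unbounded. These probabilities need no cost assumption.

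**5. What a percentile interval of R would look like.** Normal draws with r = 0.5, an assumed net saving of $500 with SE $1,500, and cost and effect uncorrelated:

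- ΔE = 1.625: interval about −$3,090 to +$1,970 per point; 0.24% of draws have ΔE ≤ 0.
- ΔE = 0.81: interval about −$14,200 to +$12,000 per point; draws are 58% cheaper and better, 34% dearer and better, 5% cheaper and worse, 3% dearer and worse.

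At the design effect the upper limit still has a meaning, because the denominator is almost always positive. The negative limit has no ordering meaning in either case. With an assumed cost SD of $10,000 and a saving of $1,000, the interval at 1.625 points is about −$3,200 to +$950.

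**The case against.** The ratio is not the only economic result. The 12-month cost model is reported with 95% confidence intervals, the mixed models give the SF-36 group differences, and the direct cost of the intervention is to be estimated. A reader might infer that the plan cannot tell a dominant TMH from a dominated one. The documents do not support that: these separate results show much of which quadrant the trial falls in. What they lack is a confidence interval for net cost including TMH cost, and the joint uncertainty of cost and effect.

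A reader might also infer that any bootstrap interval is unreadable if the hypotheses hold. That is too strong. At the design effect only 0.24% of draws have a non-positive denominator (about 0.03% at the 2-point clinically significant difference), so the upper limit can be read. The 20% in step 4 is essentially one minus the planned power, and falls to 7% at 2 points. The plan does not say what is bootstrapped; resampling cost-effect pairs would fit its sentence, so this is underspecification rather than a planned error.

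Nor do the documents say that the effect is taken at month 12 alone, which would count a gain that fades after 6 months as zero. No time point is given.

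Finally, the narrower numerator in the sentence could avoid a negative ratio. It would do so by leaving out the cost offset that Objective 3 sets out to determine, and it conflicts with the formula beside it. What stands after all this is the sign and order problem under the displayed formula, and the missing decision rule.

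**Conclusion.** The point holds as a cheap improvement to a secondary objective. Under the displayed formula, with opportunity costs aside, the hypothesised outcome gives a zero or negative ratio. It is strictly negative only if savings exceed TMH cost, and its size then has no valid order. This follows from the formula and the hypotheses alone.

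The numerical size is conditional. The 20%, 71% and 95% figures rest on PCS as the effect measure and on the assumed correlation of 0.5; at the design effect the range is 5% to 34% for correlations of 0.7 to 0.3. All dollar intervals are illustrations, since the documents give no costs. The primary efficacy analysis and the sample size are not affected.

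**What to change.** In Section 8.0, Objective 3:

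1. Define the cost increment once, as net cost including TMH cost, and make the sentence and the formula agree.
2. Report incremental net cost and incremental effect separately with 95% CIs. State that the bootstrap resamples patient-level cost-effect pairs, and show them on the cost-effectiveness plane.
3. Report incremental net benefit (value per unit × effect difference − net cost difference) with a 95% CI over a stated range of values, with an acceptability curve. Give a ratio only when both differences are positive; otherwise state which arm dominates, or report the net saving and the effect lost.
4. Name the effect measure and its time window, and match the window to the 12 months of cost. One option is the area under SF-36-based utility at baseline, 6 and 12 months; the section already cites the utility conversion.

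The cost is revised wording and a few lines of code on data already being collected. The one real demand is that a range of values per unit of effect must be stated in advance, and the documents give none.

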Non-neurologically injured patient’s health-related quality of life will be assessed using the Medical Outcome Study Short Form (SF-36). This scale has eight components (physical functioning, role-physical, bodily pain, general health, vitality, social functioning, role-emotional, and mental health) that are aggregated into a Physical Component Summary (PCS) and a Mental Component Summary (MCS). Expected scores on the PCS of the SF-36 are 40 (SD 5) at baseline, 49 (SD 5) at 6-months,

and 51 (SD 5) at 12-months. A difference of more than 2 would be considered clinically significant. Functional status prior to admission and 12 months after enrollment will be assessed using the Activities of Daily Living (Katz scale) and Instrumental Activities of Daily Living (Lawton Scale).

Self-reported Mood and Anxiety symptoms

We will use the Patient Health Questionnaire-9 (PHQ-9) and Generalized Anxiety Disorder Scale (GAD-7) to determine the impact of the intervention on non-neurologically injured patient's mood and anxiety. The PHQ-9 is a nine-item depression scale with a total score from 0 to 27 and the GAD-7 is a seven-item anxiety scale with a total score from 0 to 21. Both of these scales are derived from the Patient Health Questionnaire, have good internal consistency, and test-retest reliability as well as convergent, construct, criterion, procedural and factorial validity for the diagnosis of major depression and general anxiety disorder.^{54,57}

Acute Health Care Utilization (Secondary Objective).

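### The cost-effectiveness ratio has two conflicting definitions: the sentence leaves out health care costs, and the formula adds opportunity costs that can reverse its sign on whether savings offset the cost of TMH

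*Combined protocol and SAP*

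**What the plan says.** Secondary hypothesis 2 (section 2.0) predicts "Savings in healthcare utilization in the intervention arm that will offset the intervention costs". Section 8.0, Objective 3, gives the cost-effectiveness analysis the same purpose: "to determine if changes in health care utilization offset the intervention costs between treatment arm and usual care". The costing method follows: the plan will "estimate direct costs of the interventions and health care spending from a Medicare payment perspective". The text then broadens. It describes TMH as an intervention "which requires healthcare and non-healthcare resources for delivery (e.g., therapists or transportation) and caregiver assistance", and says that lost economic opportunity and recovery time can be given a dollar value.

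The ratio itself is introduced as "the incremental cost to achieve a clinically meaningful change in SF-36 scores due to the interventions, i.e., the cost-effectiveness (CE) ratio". In words, it "is the difference in intervention costs of the treatment arms, divided by the difference in effectiveness between groups". That sentence is joined by the word *or* to a formula:

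- numerator: the TMH intervention cost plus a delta term covering health care and opportunity costs together;
- denominator: SF-36 change under TMH minus SF-36 change under usual care.

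The same section also plans a gamma, log-link regression of total healthcare cost over 12 months with 95% confidence intervals, sensitivity analyses and bootstrapping. For the PCS of the SF-36, section 5.0 (Outcome Measures) states: "A difference of more than 2 would be considered clinically significant".

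**The concern.** The sentence and the formula are presented as the same quantity, but their numerators differ. Neither matches the payer perspective the section sets. The sentence leaves out health care spending, which is where any saving would appear. The formula includes spending but adds opportunity costs, which Medicare does not pay.

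At stake is the answer to a named secondary hypothesis. If the definition is left open, it could be settled after the costs are known, and the sign of the reported ratio may depend on the choice. Nothing in the primary analysis, the alpha or the sample size depends on this point.

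**Working it through.** **Inputs.** The documents state no cost, ratio or threshold in dollars, so there is no figure of the plan's own to reproduce. Let:

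- C = between-arm difference in intervention cost;
- H = between-arm difference in health care cost (negative means TMH saves);
- O = between-arm difference in opportunity cost;
- E = between-arm difference in SF-36 change.

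**Definitions.**

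- Sentence: C / E
- Formula: (C + H + O) / E
- Medicare payment perspective: (C + H) / E
- Offset hypothesis: C + H ≤ 0

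**Algebra, with no dollar assumption.**

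1. Sentence and formula agree only if H + O = 0.
2. The sentence contains no H, so it takes the same value whatever TMH saves.
3. The formula matches the payer perspective only if O = 0. Its numerator has the opposite sign to C + H whenever O is opposite in sign to C + H and larger in absolute size.
4. Multiplying a ratio by 2 changes its size but never its sign.
5. If E < 0, the sign of every version reverses, so offset has to be read from C + H itself.

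**Illustration.** C, H and O are assumed. E is set to 0.325 × 5 = 1.625 PCS points, from the detectable effect of 0.325 SD (section 8.0, Sample Size and Power) and the PCS SD of 5 (section 5.0). C = $2,000 throughout.

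| | Case 1: H = -$1,000 | Case 2: H = -$2,500 |
|---|---|---|
| C + H | +$1,000 (not offset) | -$500 (offset) |
| Sentence, C / E | 2,000 / 1.625 = $1,231 | 2,000 / 1.625 = $1,231 |
| Payer, (C + H) / E | 1,000 / 1.625 = $615 | -500 / 1.625 = -$308 |
| Formula, O = -$1,500 | -500 / 1.625 = **-$308** | -2,000 / 1.625 = -$1,231 |
| Formula, O = +$1,500 | 2,500 / 1.625 = $1,538 | 1,000 / 1.625 = **$615** |

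All ratios are per PCS point. The two bold entries have the wrong sign for the offset question. In case 1 the formula looks cost-saving although savings do not cover TMH. In case 2 it looks like a net cost although they do. From item 3, the sign flips in case 1 once O is below -$1,000, and in case 2 once O is above +$500.

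If the SF-36 difference went against TMH by one point (E = -1), case 1 from the payer perspective would read 1,000 / (-1) = -$1,000. That is negative with no offset.

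**Unit.** The formula divides by the raw SF-36 difference, so it gives cost per point. If the score is PCS and a meaningful difference is 2 points, the cost of a meaningful change is twice that: case 1 from the payer perspective goes from $615 to 2 × 1,000 / 1.625 = $1,231. (That this equals the sentence's figure is a coincidence of H being half of C.) Because the threshold is more than 2, a per-point figure carrying the plan's label is at least two-fold too small.

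**The case against.** The best defence is that the ratio is not the plan's only route to the offset question. Intervention costs and health care spending are to be estimated separately, and the 12-month cost regression gives the health care difference with an interval. That stands. A reader might infer that the plan cannot answer the offset question at all, and the documents do not support that: the ingredients are there. What is missing is any statement that the regression result will be set against intervention cost, or a named net-cost quantity. Sensitivity analysis and bootstrapping do not say which ratio is the main one.

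Four other stronger readings also fail:

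- *The per-point scale hides an offset.* It cannot, because a positive constant leaves the sign alone. It is a labelling error.
- *Better function is counted twice in favour of TMH.* Dollar values for recovery might overlap with SF-36 change, but the plan does not itemise the opportunity-cost term. The non-healthcare resources and caregiver help it lists could equally count against TMH.
- *The two-fold understatement is general.* It holds only if PCS is the denominator. The plan also has the MCS, and the economic text mentions utility from the SF-36.
- *There are three rival numerators.* The perspective statement says how costs are estimated and does not define a ratio. A further general phrase, incremental cost over incremental effect, is compatible with the formula. The firm conflicts are sentence against formula, and formula against perspective.

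It is also fair to say that the dollar inputs were chosen to show a sign reversal. They show that it can happen, not how likely it is.

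**Conclusion.** The point holds for the ratio as written. The two definitions agree only when the health care and opportunity-cost differences sum to zero. The sentence cannot register savings. The formula goes beyond the stated payer perspective and can give the wrong sign on offset in either direction. These conclusions rest on algebra alone. Their size in dollars cannot be known from the documents: in the illustration, case 1 runs from -$308 to $1,538 per point across the definitions and the assumed range of O, against $615 for the payer perspective.

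The unit mismatch is secondary and, at two-fold or more, conditional on PCS. The score and time point for the denominator are not named. This is a wrong rule for a secondary objective and should be corrected before cost data are analysed.

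**What to change.** 1. Make the sentence and the formula agree. For the main ratio, use a numerator that matches the stated perspective: (intervention cost + health care spending) in TMH minus the same items in usual care. Usual care patients also receive the Initial Case Review, the letter to primary care and education (section 5.0), so their cost should be netted out.
2. Report that net payer cost on its own, with a bootstrap interval, as the test of offset. Do not read offset from the sign of the ratio.
3. Move opportunity and caregiver costs to a separate analysis labelled as societal perspective, with the items and their valuation listed. Declaring a broader main perspective would also reconcile the text, provided net payer cost is still reported separately.
4. Name the SF-36 score (PCS, MCS or utility) and the time point, and define delta, which is a within-arm change in the denominator but has to be a between-arm difference in the numerator.
5. Either call the result cost per point, or scale it by the meaningful difference for the named score.

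The cost is SAP wording and one extra tabulation from costs already being estimated. The main ratio may become more or less favourable to TMH.
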